9.6. SERIOUSNESS, RELATIONSHIP AND SEVERITY OF AEs

Missing seriousness, severity and relationship of AEs that have been queried and remain missing after such, will be treated ‘worst case’ for presentation filtering purposes as follows:

- Missing seriousness: Will be considered as serious and included in the SAE displays.
- Missing relationship: Will be considered as related and included in the related AE displays.
- Missing severity:
 - If subject has died, will be considered as Grade 5 severity across all associated displays.

- If subject has not died but subject had intervention indicated for the AE, will be considered as Grade 4 severity across all associated displays.
- If none of the previous conditions are met, will be considered as Grade 3 severity across all associated displays.

9.7. VISIT WINDOWS/UNSCHEDULED VISITS

No mapping/renaming of visits (unscheduled or otherwise) will be done for this study. That is, only regular scheduled visit data will be used for summarization in tables. However, all collected data will be listed.

Unscheduled visits will be considered eligible for Baseline values. Unscheduled visit results will also be considered eligible for testing of potentially clinically significant (PCS) values (laboratory, Electrocardiogram (ECG) and vital signs).

10. STATISTICAL ANALYSIS METHODS

10.1. SUBJECT DISPOSITION

The following disposition related items are planned to be listed using the protocol part and analysis set indicated in parentheses:

- Screening failures (Part 1 – All subjects)
- Screening failures (Part 2 – All subjects)
- Randomized subjects (Part 1 – FAS)
- Randomized subjects (Part 2 – FAS)
- Unblinded subjects, if any (Part 1 – FAS)
- Unblinded subjects, if any (Part 2 – FAS)
- Inclusion/Exclusion violations (Part 1 – FAS)
- Inclusion/Exclusion violations (Part 2 – FAS)
- Subject completion/discontinuation information (Part 1 – FAS)
- Subject completion/discontinuation information (Part 2 – FAS)
- Subject analysis set inclusions (Part 1 – FAS)
- Subject analysis set inclusions (Part 2 – FAS)
- Subject deviations (Part 1 – FAS)
- Subject deviations (Part 2 – FAS)

The following disposition related items are planned to be tabulated using summary and descriptive statistics as applicable, by treatment groups and baseline AD severity stratifications (for Part 2 only), using the protocol part and analysis set indicated in parentheses:

- Subject completion/discontinuation information (Part 1 – All subjects). Including breakdown by reason for subject discontinuation.
- Subject completion/discontinuation information (Part 2 – All subjects). Including breakdown by reason for subject discontinuation.
- Subject analysis set inclusions (Part 1 – All subjects). Including reason for exclusion from analysis set, if required.
- Subject analysis set inclusions (Part 2 – All subjects). Including reason for exclusion from analysis set, if required.
- Subject deviations (Part 1 – FAS).
- Subject deviations (Part 2 – FAS).

The data for these presentations are obtained from the following electronic Case Report Forms (eCRFs):

- Informed Consent
- Screen Failure
- Inclusion Exclusion Criteria
- Randomization
- End of Study

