7 DISCONTINUATION OF STUDY DRUG AND PATIENT DISSCONTINUATION/WITHDRAWAL

A patient may stop study drug or withdraw from the study at any time for any reason or may be withdrawn at any time at the discretion of the investigator for safety, behavioral, compliance, or administrative reasons. This is expected to be uncommon.

Reasons for removal from study drug and/or from the study include any of the following:

- Liver injury (see Section 7.1 below)]
- Cardiac changes (see Section 7.2 below)
- Adverse events
- Pregnancy
- Protocol deviation
- If the patient meets an exclusion criterion (either newly developed or not previously recognized) that poses a greater risk to the patient with continued participation
- If, in the investigator's opinion, continuation of the study would be harmful to the patient's well being
- Sponsor decision
- Patient request to discontinue study drug or withdraw consent for study participation
- Death
- Lost to follow-up

At the time of discontinuing from the study, if possible, an E/D visit should be conducted, as shown in the SoA (Table 1 and Table 2). See Table 1 and Table 2 for data to be collected at the time of study discontinuation.

Every effort should be made by the site to follow the patient and maintain scheduled safety visits through the Day 104 visit if at all possible, even for patients who voluntarily withdraw their consent.

If the patient withdraws consent for disclosure of future information, the sponsor may retain and continue to use any data collected before such a withdrawal of consent.

If a patient withdraws from the study, he/she may request destruction of any samples taken and not tested, and the investigator must document this in the site study records.

Protocol TB006AD2102

Protocol Date and Version: 15 Oct 2021; v 3.0

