9.4.2 Part 1 Primary Endpoints

9.4.2.1 Safety and Tolerability

All AEs will be coded using the most recent version of MedDRA. The incidence of AEs will be summarized by SOC and PT. Similar summaries will be produced for AEs by severity, SAEs, treatment related AEs, and AEs leading to discontinuation. AEs are collected from the first dose of study drug, thus all AEs are considered treatment emergent AEs.

The ECG results will be presented by visit, summarizing the continuous measurements based on the average of triplicate values, including the QT, QTc, QRS, RR, PR intervals, as well as change from baseline values, and clinically significant changes in heart rate and rhythm.

Reported values and change from baseline values of hematology, clinical chemistry and urinalysis (and the determinations relevant to the normal ranges and appropriate clinically significant or CTCAE toxicity gradings) will be summarized by laboratory test for each assessment day, using appropriate descriptive statistics.

Vital signs (systolic and diastolic blood pressure, pulse rate, respiratory rate, and oral temperature) will be summarized by assessment day showing absolute values, change from baseline values, and clinically significant changes (including orthostasis) using appropriate descriptive statistics.

Physical and neurological examinations will be summarized by assessment day showing shift from baseline.

Protocol TB006AD2102

Protocol Date and Version: 15 Oct 2021; v 3.0

The C-SSRS assessments will be presented in a by-subject listing.

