9.4.4 Part 1 Other Analyses

The patient disposition showing numbers randomized, treated, completed, treatment discontinuation, and discontinued from the study will be summarized. For those patients who discontinued the study or the study treatment prematurely, the reason for discontinuation will be summarized.

All patient data will be reviewed for the occurrence of protocol deviations. Summaries will be presented showing the numbers of patients with each class and type of deviation.

Demographic variables to be summarized will include age, gender, race, ethnicity, height, weight, and BMI.

Baseline characteristics to be summarized will include medical history and viral serology. Prior and concomitant medications will be summarized showing the number and percentage of patients taking each medication. Medications will be coded using the World Health Organization Drug Dictionary preferred name.

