8. CHANGES IN CONDUCT OR PLANNED ANALYSES FROM THE PROTOCOL

The following analyses described in this SAP are not mentioned in the study protocol:

- Assessment of dose proportionality (see Section 10.5: Pharmacokinetics).

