12.1. ADVERSE EVENTS

The following AE definitions are applicable to both protocol parts of this study:

- AE reporting period: Defined from start of first dose of study drug infusion on Day 1 up to and including End of Study.
- AE: Any untoward medical occurrence in a subject.
- Treatment-emergent AE (TEAE): Defined as any AE that started on or after first dose of study drug infusion within the studies' AE reporting period.
- SAE: Defined as any AE that is indicated as serious on the AEs Details eCRF, as per investigator's assessment.
- Related AE: Defined as any AE that is indicated as related to study drug on the AEs Details eCRF, as per investigator's assessment.
- AE leading to discontinuation: Defined as any AE that has an "other action taken" indicated as "withdrawn from study" on the AEs Details eCRF.

All AEs will be coded using the MedDRA version 22.1, Sep 2019. The following AE items will be listed separately for each protocol parts using the SAS:

- All AEs
- AEs leading to study discontinuation
- Serious AEs
- AEs leading to death (if applicable)

The following items are planned to be presented in summary tables showing event incidence and corresponding subject count, experiencing said AE/AE type using the SAS, by treatment groups using SAS:

- AE overview, including row items for frequency of subjects [n(%)] experiencing:
 - At least one AE
 - AEs by toxicity grade
 - Grade 1
 - Grade 2
 - Grade 3
 - Grade 4
 - Grade 5
 - Serious AEs

- Related AEs
- Non-related AEs
- AEs leading to study discontinuation
- AEs leading to death
- AEs by system organ class (SOC) and preferred term (PT)
- AEs by descending incidence of PT
- AEs by toxicity grade (Common Terminology Criteria for Adverse Events [CTCAE] grading)
- Related AEs by SOC and PT
- Related AEs by descending incidence of PT.
- Serious AEs
- AEs resulting in death
- AEs leading to study discontinuation

Only TEAEs will be used for summarization of all tables, but for listing all AEs will be counted. The TEAE status will be derived using the AE start and stop dates as per definition provided at the start of this section. For partial dates see [Section 9.4.1](#).

The data for these presentations will be obtained from the Adverse Events Details eCRF.

AE assignment to CTCAE toxicity grades is explained in [Table 2](#) below.

Table 2. CTCAE Grades

Grade	Grade Description	Grade Details

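### For patients who stop study drug early but stay in follow-up, the SAP text guarantees no summary of the stop

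*SAP*

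**What the plan says.** **Disposition.** Protocol 9.4.4, on Part 1, states: "The patient disposition showing numbers randomized, treated, completed, treatment discontinuation, and discontinued from the study will be summarized". It adds: "For those patients who discontinued the study or the study treatment prematurely, the reason for discontinuation will be summarized". SAP 10.1 tabulates subject completion and discontinuation for each part, "Including breakdown by reason for subject discontinuation". It then states: "The data for these presentations are obtained from the following electronic Case Report Forms (eCRFs"; the forms listed are Informed Consent, Screen Failure, Inclusion Exclusion Criteria, Randomization and End of Study. No dosing or end-of-treatment form is named. SAP Section 8, on changes from the protocol, opens "The following analyses described in this SAP are not mentioned in the study protocol" and lists one item, dose proportionality.

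**Adverse events.** Protocol 9.4.2.1 says: "Similar summaries will be produced for AEs by severity, SAEs, treatment related AEs, and AEs leading to discontinuation". It does not say whether discontinuation of drug or of study is meant. SAP 12.1 settles this: "AE leading to discontinuation: Defined as any AE that has an" entry of withdrawn from study in the other-action-taken field. Its tables and listing are titled as AEs leading to study discontinuation.

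**Compliance.** SAP 10.7 divides doses received, partial doses included, by doses expected between the first infusion and the last dose date. It reports descriptive statistics and the share of patients at 80% or more. Last dose date is not defined. The section also plans a dose-by-dose listing, a compliance listing and a table of dose level exposure.

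**Stopping drug and leaving the study.** Protocol Section 7 treats these as different events: "A patient may stop study drug or withdraw from the study at any time for any reason". It asks sites to keep scheduled safety visits going to Day 104 where possible. Appendix 3 allows a patient who has permanently stopped drug to remain for follow-up assessments.

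**The concern.** The treatment is a course of 5 weekly infusions. Safety and tolerability of multiple doses is a primary objective in Part 1 and a secondary objective in Part 2. How many patients could not or did not finish the course, and why, is a basic tolerability result.

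Three separate choices in the SAP leave the same patient out: one who stops drug and stays. The disposition table has no row for that patient. The AE table does not count the event that stopped the drug. The compliance figure may show full compliance. Under Protocol 4.4 a patient who attends every visit through Day 104 has completed the study, so someone who received one infusion could be summarised as a completer with 100% compliance.

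**Working it through.** **1. Disposition and AE text, side by side**

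| Item | Protocol | SAP |
|---|---|---|
| Study discontinuation, with reasons | Required for Part 1 (9.4.4) | Planned for Parts 1 and 2 (10.1) |
| Treatment discontinuation, with reasons | Required for Part 1 (9.4.4) | Not planned in 10.1; omission not listed in Section 8 |
| AEs leading to discontinuation | Required; drug or study not specified (9.4.2.1) | Study withdrawal only (12.1) |

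The first gap is an undeclared departure from the protocol. The second is a permissible choice that leaves drug stops uncounted.

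**2. Which last dose date?** SAP 9.4.1, Table 1, uses the date of last dose of study drug as an actual date. The only source named for compliance is the Study drug infusion form. Both point to the last dose received. The other reading is the date of the scheduled fifth dose.

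**3. Compliance for one patient.** Inputs: 5 planned infusions on Days 1, 8, 15, 22 and 29 (schedule of activities), and a permanent stop after infusion k with no earlier skip.

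- Last dose received: k/k × 100
- Scheduled fifth dose, or the planned course as denominator: k/5 × 100

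| Stop after infusion | Last dose received | Of 5 planned | Opposite sides of 80%? |
|---|---|---|---|
| 1 | 1/1 = 100% | 1/5 = 20% | Yes |
| 2 | 2/2 = 100% | 2/5 = 40% | Yes |
| 3 | 3/3 = 100% | 3/5 = 60% | Yes |
| 4 | 4/4 = 100% | 4/5 = 80% | No, passes both |

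A patient who misses only Day 15 receives 4 of 5 and scores 4/5 = 80%. On the received-dose reading the ranking can therefore invert: one infusion scores 100%, and four infusions with a mid-course skip score 80%.

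**4. Effect on a Part 1 dose group.** Six patients per group receive TB006. Suppose one stops after infusion k and the other five complete.

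- Received-dose reading: mean = 600/6 = 100%; share at 80% or more = 6/6 = 100%
- Of 5 planned: mean = (500 + 20k)/6 = 86.7, 90.0, 93.3 and 96.7% for k = 1, 2, 3 and 4
- Share at 80% or more, of 5 planned: 5/6 = 83.3% for k = 1 to 3, and 6/6 = 100% for k = 4

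One patient is 1/6 = 16.7% of such a group and 1/58 = 1.7% of a Part 2 arm. These are illustrations: the documents give no stopping rate, and Protocol Section 7 expects stopping to be uncommon.

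**The case against.** Much can be said for the plan as it stands.

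- **Most of the information exists.** A patient who stops drug and leaves the study is tabulated with the reason. Every dose is listed with date and time, compliance and AEs are listed, and with eight patients per Part 1 group a reader can find each stop. The dose level exposure table may show infusion counts, though the SAP does not say so; layouts are left to mock shells that are not available here. This stands, and it confines the gap to summaries of patients who stop drug and stay.
- **The AE table is correctly labelled.** If one of six stops drug and stays, 0/6 is the right count of study withdrawals. A reader might infer that the table departs from the protocol or reports a wrong rate. Neither follows: Protocol 9.4.2.1 leaves the term open, and the SAP defines it and titles the outputs accordingly. What remains is a figure that is not given.
- **On-treatment compliance is a coherent measure.** The protocol prescribes no denominator. This stands if the ratio is labelled as such and the end date is defined, and at present it is neither.
- **Liver stops.** A reader might infer that every liver-related stop disappears. That is too strong. Protocol 7.1 leaves discontinuation to the investigator's consideration, Appendix 3 lists it as a required action, and restart is possible with approval. Those passages need reconciling with each other, but the reporting gap does not depend on which governs. Marked liver abnormalities have their own tables in SAP 12.2.
- **Dose escalation.** Protocol 6.2.1 names discontinuation due to AEs among the escalation variables, so a reader might infer that the SAP weakens those decisions. It does not: under Protocol 4.1 and 9.6 the Safety Review Committee uses accruing data, not these tables.

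**Conclusion.** The point holds as a minor reporting correction. The firmest part is the Part 1 disposition: a summary that the protocol requires is absent from the SAP and its omission is not declared. The AE definition is not a departure but leaves a tolerability gap. The compliance result rests on reading last dose date as the last dose received. The SAP supports that reading better but does not state it; on the other reading the score is already out of 5 and only the wording needs repair.

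The size for one patient is 100% compliance in place of 20, 40, 60 or 80%, with a change of side at the 80% threshold only for stops after infusion 1, 2 or 3. How many patients this would touch cannot be derived from the documents. A reader should not infer bias between arms or a changed efficacy result: no estimate, test or analysis set depends on these tables.

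**What to change.** - **SAP 10.1:** add the Part 1 treatment-discontinuation row with reasons. The same row is sensible for Part 2, although the explicit protocol requirement cited here is for Part 1.
- **SAP 10.7:** use the 5 planned infusions as denominator, or keep the current ratio, label it on-treatment compliance and define last dose date. In either case, tabulate infusions received (1 to 5) with partial infusions shown separately. Partial doses count as received, and a stop after infusion 4 still scores 80% against plan, so no single percentage replaces that table.
- **SAP 12.1:** add a table and listing of AEs leading to discontinuation of study drug beside the study-withdrawal ones.

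The cost is a few table rows, slightly lower reported compliance and a check of the case report form. SAP 10.1 names no end-of-treatment form, so reasons for stopping drug may not be coded for patients who stay. Protocol 10.2.3 has the investigator record the action taken for each AE, and the SAP's reference to other action taken suggests a separate field for study drug. The form specification is not available here, so this needs confirming. If no such field exists, the reason would have to come from the AE page or from a form update.

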10.2. DEMOGRAPHICS AND BASELINE CHARACTERISTICS

The following demographics and baseline characteristic items will be listed using SAS for both protocol parts:

- Subject demographics:
 - Age
 - Sex
 - Race
 - Ethnicity
- Baseline vital characteristics:
 - Height (cm)
 - Weight (kg)
 - BMI (kg/m²)
- Substance usage, including checking for:
 - Tobacco/nicotine use
 - Alcohol use
 - Drug use

The above demographic, baseline characteristics and substance use items are planned to be tabulated using summary and descriptive statistics as applicable, by treatment groups for SAS.

The data for these presentations will be obtained from the following eCRFs:

- Demography
- Physical Examination (for baseline height/weight)
- Medical History (for substance usage medical history)
- Drug and Alcohol Screening

The following items will be derived:

- Body mass index (BMI) at Baseline:

$$\text{Baseline BMI} = \text{Baseline weight (kg)} \div [\text{Baseline height (m)}]^2$$

10.3. MEDICAL HISTORY AND VIRAL SEROLOGY

The medical history terms will be coded using the Medical Dictionary for Regulatory Activities (MedDRA) version 22.1, Sep 2019.

The following medical history and viral serology baseline characteristic items will be listed using SAS for both protocol parts:

- Medical history:
 - Medical conditions or allergies reported
- Viral serology
 - HBsAg
 - IgM anti HBC
 - anti HCV
 - HIV
- COVID-19 status

The above medical history is planned to be tabulated using summary statistics, by treatment groups using SAS.

The data for these presentations will be obtained from the following eCRFs and external data:

- Medical History
- Viral Serology
- Laboratory Data

10.4. PRIOR AND CONCOMITANT MEDICATIONS AND PROCEDURES

A prior medication or procedure is defined as having started and ended prior to first dose of study drug infusion. Conversely, a concomitant medication or procedure is defined as either having started prior to first dose of study drug infusion and ended on/after first dose of study

drug infusion, is ongoing at Baseline or, having started on/after first dose of study drug infusion. Medications will be coded using the World Health Organization-Drug Dictionary (WHO-DD) Global Sep 2019 B3/C3 format.

Listings of prior and concomitant medications/procedures will be presented for both protocol parts as recorded in the eCRF (SAS).

Summary tables by WHO-DD Anatomical Therapeutic Chemical (ATC) level 3 and preferred name will be presented, by treatment groups on the following items:

- Prior medications/procedures (Part 1 – SAS).
- Prior medications/procedures (Part 2 – SAS).
- Concomitant medications/procedures (Part 1 – SAS)
- Concomitant medications/procedures (Part 2 – SAS)

The data for these presentations will be obtained from the Concomitant Medications Details eCRF.

The Prior/Concomitant status will be derived using the medication start and stop dates as per definition provided at the start of this section. For partial dates see Section 9.4.1.

10.5. PHARMACOKINETICS

The following PK listings are planned for presentation (PKS) for both protocol parts:

- TB006 plasma concentration levels
- TB006 CSF concentration level (Part 1 only)
- Pharmacokinetic parameters of plasma TB006
- Dose-normalized plasma exposure PK parameters (AUCs and C_{max}) – (Part 1 only).

The following descriptive summary tables are planned to be presented for subjects who received TB006 (PKS), by treatment groups and baseline AD severity stratifications (for Part 2 only):

- Plasma concentration of TB006 at each time points
- CSF concentration of TB006 at each time points (Part 1 only)
- Plasma PK parameters
- Dose-normalized exposure PK parameters (AUCs and C_{max}) (Part 1 only, Days 1, 8, and 29, as applicable)
- Power model slope estimate for dose proportionality assessment (including 95% CI) (Part 1 only)

Figures of the following PK items are planned for presentation (PKS) for both protocol parts:

- Overlaid individual plasma concentration versus time plots (linear and semi-logarithmic scale) by treatment groups

- Overlaid mean plasma concentration versus time plots, presented by treatment groups (linear scale with and without SD)
- Overlaid mean plasma concentration versus time plots, presented by treatment groups (semi-logarithmic scale with and without SD)
- Boxplots of dose-normalized PK parameters (AUCs and C_{max}), grouped by treatment groups grouped within each figure (Part 1 only, Days 1, 8, and 29, as applicable)
- Scatterplots of PK parameters (AUCs and C_{max}), versus dose (as part of power model results), by treatment groups (Part 1 only, Days 1, 8 and 29, as applicable)

Assessment of dose proportionality will be performed by PK Day (Day 1, 8, and 29, as applicable) and will not be based strictly on statistical rule criteria but rather, several factors will be taken into account when assessing dose proportionality, such as:

- Power model results (e.g., the slope estimate and the width of the 95% CIs)
- Graphical evaluation (box plots of dose normalized AUCs and C_{max})
- Descriptive statistics by treatment groups of dose-normalized PK parameters

Evaluations of the dose proportionality of these parameters will include using the Power Model if there will be at least 3 dose levels available. A statistical linear relationship between the ln-transformed PK parameters and the ln-transformed dose will be fitted by using a mixed model with ln-transformed dose as a covariate and random effect for intercept and subject. Here, (ln-) stands for natural logarithm. Additional predictors may be included in the model. The general form of the Power Model is described as:

$$Ln(Y) = \beta_0 + \beta \ln(Dose) + \varepsilon$$

Where, Y represents the PK parameter (AUCs and C_{max}), and β_0 is constant. This approach is usually referred to as a power model because after exponentiation:

$$Y = \alpha (Dose)^\beta$$

[figure not shown]
Note that $\beta = 1$ would correspond to perfect dose proportionality.

The following example SAS® code can be utilized and modified as needed:

```
Proc Mixed Data = <Dataset>;
  Class <subjectnum>
  Model <lnY> = <lnDose> / ddfm=kr;
  Random <intercept> / subject = <subjectnum> type=UN;
  Estimate 'Logdose - 1 unit' <lnDose> 1/CL alpha=0.05;
  ods output estimates = <estimate>;
Run;
```

Where <Dataset> is the input dataset, <subjectnum> is the subject number, <lnY> is $\ln(Y)$ (Y being the PK parameter in question, <lnDose> is $\ln(Dose)$, <intercept> is the intercept and <estimate> is the output dataset containing the estimate.

The data for these presentations will be obtained from the external PK laboratory data and eCRF.

Descriptive summary tables of biomarker levels from both plasma and CSF (for Part 1 only) collection will be presented, by treatment groups and baseline AD severity stratifications (for Part 2 only), using PDS for both protocol parts, including CFB and CFB% through end of study.

The relationship between dose, Day 29 plasma TB006 PK exposure parameters (AUC_{tau} and C_{max}), Day 36 CSF TB006 concentration and PD biomarkers listed in Section 10.6 will be assessed graphically. Scatter plots of CFB and CFB% will be presented next to another in grid format for PD endpoint values versus TB006 AUC_{tau} and C_{max} . The PD endpoints will be for timepoints Day 36 and end of study. The main measure of interest for consideration will be the CFB of PD biomarkers.

The data for these presentations will be obtained from the external laboratory data and eCRF.

